7.8.3 Vital signs

Descriptive statistics will be presented over time for absolute values and changes from baseline in each of the vital signs variables.

The time points to be presented will follow the expected data structure for each vital signs variable as follows:

- For systolic and diastolic BP, three measurements are planned to be captured at each of pre-dose (all weeks), 15 minutes post-dose (selected weeks only) and 60 minutes post-dose (all weeks). The descriptive summary will therefore display all relevant time points within week. Multiple measurements at each time point will be handled using the rules in [Section 6.7](#).
- For pulse rate, one measurement is planned to be captured at each of pre-dose (all weeks), 15 minutes post-dose (selected weeks only) and 60 minutes post-dose (all weeks). The descriptive summary will therefore also display all relevant time points within week.
- For respiratory rate and temperature, a single measurement is expected to be captured at each week. The descriptive summary will therefore not display a time point within week.

Body weight and waist circumference over time are covered entirely within the relevant efficacy sections, and are not considered further as part of safety.

7.8.4 ECG

Abnormal findings will be reported as baseline conditions (at screening) or as AEs (during the trial) if judged clinically relevant by the investigator.

The ECG recordings will be centrally evaluated and rated as normal, abnormal, or not evaluable.

All derivations relating to 12-lead ECG variables are given in [Section 5.4.1](#).

Occurrences of values above thresholds will be flagged in the listings. For QTcB and RR, only listings will be provided.

Quantitative variables

Descriptive statistics will be presented over time for absolute values and absolute changes from baseline in the following quantitative ECG variables: QTcF, HR, QT, QRS, PR. Percentage changes used to derive the categorical variables (see below) will be listed only.

Categorical variables

Frequency tables will be provided for the categorical variables described below, which are determined from the specified quantitative ECG variables:

- New onset (meaning that this or a higher category was not present any time at baseline) of maximum QTcF interval > 450 to 480 msec, > 480 to 500 msec, or > 500 msec on treatment.
- New onset (not present any time at baseline) of uncorrected QT interval > 500 msec at any time on treatment
- Maximum change from baseline of QTcF ≤ 30 msec, > 30 to ≤ 60 msec, or > 60 msec on treatment.
- Maximum change from baseline of QT ≤ 60 msec, or > 60 msec on treatment.

For assignment of a particular patient to one of the above categories, all available time points on-treatment will be considered.

The occurrence of any of the following will be considered as “notable findings” and summarised using frequency tables:

- New onset (not present any time at baseline) of uncorrected QT interval > 500 msec at any time on treatment
- New onset of QTcF interval > 500 msec at any time on treatment
- Change from baseline of QTcF > 60 msec at any time on treatment
- Percentage change from baseline of HR $\geq 25\%$, when corresponding on-treatment value of HR is > 100 beats/min, or percentage change from baseline of HR $\leq -25\%$, when corresponding on-treatment value of HR is < 50 beats/min, at any time on-treatment
- Percentage change from baseline of PR $\geq 25\%$, when corresponding on-treatment value of PR interval is > 200 msec, at any time on treatment
- Percentage change from baseline of QRS $\geq 10\%$, when corresponding on-treatment value of QRS duration is > 110 msec, at any time on treatment.

Frequency tables will also include morphological findings (determined and categorized based on SDTM terminology) that might be attributable to treatment. In particular, new onsets of findings not present at baseline will be explored. A morphological finding observed on treatment that was not reported at baseline will be categorized as a ‘new onset’ of this finding.

For all patients with any notable finding in ECG intervals, a separate listing will be created as end-of-text display, and the corresponding time profiles will be shown.

A shift table will be produced for QTcF, summarising the shifts from baseline to the maximum value on treatment, and displaying categories “ ≤ 450 msec”, “> 450 to 480 msec”, “> 480 to 500 msec and “> 500 msec”.

A scatter plot of QTcF at baseline and the maximum change from baseline (based on all on-treatment values as defined in [Section 6.1.6](#), and the maximum evaluated regardless of whether these were selected based on visit windows described in [Section 6.7](#)) will be produced. The plot will include diagonal reference lines for absolute QTcF equal to 450 msec, 480 msec and 500 msec, as well as horizontal reference lines for QTcF maximum changes from baseline equal to 30 msec and 60 msec.

Appropriateness of heart rate correction methods of QT interval

To evaluate the appropriateness of the heart rate correction methods, the slope of the relationship of the (untransformed) QTcF interval versus RR interval will be estimated for off-drug values and for each BI 456906 maintenance dose group separately by applying a random coefficient (random slope and intercept) model. Off-drug values for this purpose are defined as only values (either baseline or on-treatment values as defined in [Section 6.1.6](#)) from patients randomised to placebo, since patients randomised to BI 456906 dose groups are expected to have a single ECG at baseline only, and therefore cannot contribute a slope for estimation of an off-drug random effect for this. For the BI 456906 maintenance dose group analyses, only on-treatment values will be used, and these will be included regardless of BI 456906 dose (i.e. data from the dose escalation period will be included). The model will be fitted using the QTcF and RR pairs at each time point, using all values within the visit windows defined in [Section 6.7](#). A scatter plot of QTcF versus RR will be produced, and will include the overall regression line obtained from the model. The population estimate of the slope together with its two-sided 95% confidence interval will be displayed in a footnote to the plot.

The slope of the relationship of the log-transformed (uncorrected) QT interval versus log-transformed RR interval will be estimated for off-drug values and for each BI 456906 maintenance dose group separately by applying a random coefficient (random slope and intercept) model similar to above, with off-drug values and data selection defined in the same way. A scatter plot of log(QT) versus log(RR) will be produced, and will include the overall regression line obtained from the model. The population estimate of the slope together with its two-sided 95% confidence interval will be displayed in a footnote to the plot.

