1.2 DRUG PROFILE

Mode of action

BI 456906 is a dual agonist of GLP-1 and Glucagon receptors. Targeting both GLP-1 and Glucagon signalling pathways is expected to provide synergistic clinical benefit for chronic weight management and obesity.

Simultaneous dual activation of GLP-1R and GCGR by BI 456906 is anticipated to achieve improved glycaemic control, reduction in body weight and improvement in NASH. BI 456906 leads to full activation of the GLP-1R at the predicted therapeutic exposure, but only to a partial activation of the GCGR, which seems sufficient to achieve greater weight loss than GLP-1R activation alone, without hyperglycaemia.

In a 4-week study in mice with diet-induced obesity, BI 456906 was able to induce a body weight loss greater than liraglutide. BI 456906 dose-dependently increased energy expenditure while the pure GLP-1R agonist liraglutide had no effect even at supra-therapeutic exposure. It is expected that the increased energy expenditure will contribute to a longer lasting negative energy balance than GLP-1R agonism alone, while achieving a favourable benefit/risk profile ([c14085752-05](#))

Key pharmacokinetic characteristics

Drug interactions

Data from non-clinical studies

Data from clinical studies

GLP-1R agonists are known to be associated with GI and cardiac side effects.

Multiple studies and clinical experience from GLP-1R agonists suggest that GI side effects can be mitigated by dose escalation. Rates of nausea, vomiting, and diarrhoea appeared to be dose dependent for GLP-1R agonists, and the proportion of patients reporting nausea was 20% lower in patients with dose escalation than without dose escalation [R17-4311].

Accordingly, for a number of compounds of this class it has been shown that dose escalation steps are able to significantly improve tolerability in clinical practice.

Cardiac conduction disorders were described for GLP-1R agonists in clinical trials and in the prescribing information for Saxenda [R19-1407], reported as first-degree atrioventricular block, right bundle branch block, or left bundle branch block, as well as QT-prolongation.

BI 456906 has been studied in healthy volunteers in a single rising dose trial (1404-0001). Similar to other GLP-1 agonists, nausea and vomiting were seen with increasing doses up to 1.2 mg and the study was discontinued early due to severe nausea and vomiting in a number of healthy volunteers.

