1.4.2 Risks

There is no identified risk for BI 456906, based on the toxicology programme or any clinical trials conducted for this product to date. There are three important potential risks based on other GLP-1 receptor agonists currently approved, providing information on identified and potential risks in molecules of this class. The three important potential risks include medullary thyroid cancer (c-cell carcinogenicity), pancreatic cancer, and acute pancreatitis.

The risk for patients caused by participation in the trial, including the study procedures and exposure to the study drug, are reasonably low and do not outweigh the potential benefits. The expected side effects are known to be temporary, dose dependent, easy to monitor and manageable in clinical trials.

Table 1.4.2:1 Overview over trial related risks

| Possible or known risks of clinical relevance for this trial | Summary of data, rationale for the risk | Mitigation strategy |
|--|--|---|
| Investigational Medicinal Product | | |
| Gastrointestinal disorders, or Metabolism and nutrition disorders | Well-known side effects for GLP1-R agonist-based therapies | Slow and careful dose escalation. Instructions to be given |
| Cardiac disorders | Well-known side effects for GLP1-R agonist-based therapies | Centralised Electrocardiogram (ECG) monitoring will be performed at screening, randomization and within predefined intervals during the trial, and criteria for heart rate, QT prolongation and cardiac conduction disorders are defined. |
| Acute pancreatitis | To date there is no evidence that BI456906 causes such adverse events. | An extensive safety laboratory will be performed. |
| Medullary thyroid carcinoma (MTC), or Multiple endocrine neoplasm (MEN) Type 2 | Well-known side effects for GLP1-R agonist-based therapies * Well-known side effects for GLP1-R agonist-based therapies, and well-known adverse event of rapid significant weight loss | Timely detection, evaluation, and follow-up of laboratory alterations in selected liver laboratory parameters to ensure patients' safety. |
| Acute biliary disease* | | |

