3. INTRODUCTION

As per ICH E9, the purpose of this document is to provide a more technical and detailed elaboration of the principal features of the analysis described in the protocol, and to include detailed procedures for executing the statistical analysis of the primary and secondary variables and other data.

This TSAP assumes familiarity with the Clinical Trial Protocol (CTP), including Protocol Amendments. In particular, the TSAP is based on the planned analysis specification as written in CTP Section 7 “Statistical Methods and Determination of Sample Size”. Therefore, TSAP readers may consult the CTP for more background information on the study, e.g., on study objectives, study design and population, treatments, definition of measurements and variables, planning of sample size, randomisation.

This document describes the main analysis of study 1404-0036. One interim analysis is planned for sponsor planning purposes. This is described in a separate interim statistical analysis plan, and is not addressed further in this document. The interim analysis results are not intended to be used to stop the trial, nor to make confirmatory claims. No statistical adjustments to Type 1 error are therefore considered necessary.

This TSAP is based on the 1404-0036 CTP (Version 5.0, 29APR2022), together with the latest versions of the eCRF and relevant Data Transfer Agreements (DTAs) for external vendor data.

All statistical analyses defined in this TSAP will be performed by the trial statistician (TSTAT) with support from other trial team members following unblinding of the trial at final database lock (DBL). This TSAP will be finalized and signed prior to final DBL.

All data will be cleaned and coded, all vendor data transferred (unless documented otherwise), and all eCRF pages approved by the investigator prior to DBL. A DBL meeting will be held prior to taking the final database snapshot. It will be decided at this meeting whether any open cleaning issues will be accepted or not. Important protocol deviations (IPDs) will also be finalized prior to DBL, except where unblinded dosing information after DBL is needed to confirm dose discrepancies for relevant IPDs.

SAS[®] version 9.4 or later will be used for all analysis. Where statistical analyses require the use of R instead of SAS[®], R version 4.0.1 or later will be used.

The analyses and outputs specified in this TSAP will be included in the clinical trial report (CTR) unless specified otherwise.

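### SAP 7.8.4 has no visible count of new PR above 200 msec without a 25% rise, and it limits the ECG morphology table by an undefined attribution condition

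*SAP*

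**What the plan says.** Protocol 1.2 describes cardiac conduction disorders seen with GLP-1 receptor agonists, "reported as first-degree atrioventricular block, right bundle branch block, or left bundle branch block, as well as QT-prolongation". The risk table in Protocol 1.4.2 says that "criteria for heart rate, QT prolongation and cardiac conduction disorders are defined".

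SAP 7.8.4 handles ECG conduction data as follows:

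- **PR, notable finding.** A rise from baseline of at least 25% is required, "when corresponding on-treatment value of PR interval is > 200 msec, at any time on treatment". Both conditions must hold.
- **QRS, notable finding.** A rise of at least 10% is required, "when corresponding on-treatment value of QRS duration is > 110 msec, at any time on treatment".
- **QTcF and QT.** New-onset categories are defined by absolute thresholds with no percentage condition. QTcF also has a shift table.
- **Descriptive statistics.** Absolute values and changes over time are given "in the following quantitative ECG variables: QTcF, HR, QT, QRS, PR". Values above thresholds are flagged in listings.
- **Morphology.** "Frequency tables will also include morphological findings (determined and categorized based on SDTM terminology) that might be attributable to treatment". The text adds that new onsets will be looked at in particular. It defines new onset objectively, as a finding seen on treatment but absent from the baseline report.

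SAP 3 places all analyses after unblinding at final database lock and requires the SAP to be signed before then. SAP 11 labels version 1.0 as final.

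**The concern.** First-degree AV block is in essence a PR above 200 msec, and the protocol names it as a class effect. A reader would expect a by-arm count of patients who newly cross that value. The only categorical PR count in the available text adds a 25% condition. That condition is hardest to meet for patients who start closest to 200 msec, and they are the most likely to cross.

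Morphology is the other ECG route. There, possible attribution to treatment is a condition for entering the table. In a randomised trial the comparison between arms is what informs attribution. Without a list of findings, a rule, a named decision-maker or a date, the set of rows remains open when the arms become known. What is at stake is whether a modest dose-related conduction effect appears as a patient count in a dose-finding trial that informs phase III.

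**Working it through.** The documents state no figure for PR findings, so there is nothing to reproduce.

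**Step 1: the PR rule, exact.** For baseline b, a reading is counted if PR > 200 and PR ≥ 1.25 × b. The two limits meet at b = 200 / 1.25 = 160 msec.

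- If b ≤ 160, every PR above 200 already satisfies the 25% condition, and nothing is missed.
- If 160 < b ≤ 200, a PR between 200 and 1.25 × b is not counted.

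| Baseline PR (msec) | PR needed to be counted | Rise needed |
|---|---|---|
| 170 | 1.25 × 170 = 212.5 | 42.5 |
| 180 | 1.25 × 180 = 225 | 45 |
| 190 | 1.25 × 190 = 237.5 | 47.5 |
| 200 | 1.25 × 200 = 250 | 50 |

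At any baseline up to 200 msec the rule needs a rise of more than 40 msec: 200 − b is at least 40 when b ≤ 160, and 0.25 × b exceeds 40 when b > 160.

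**Step 2: how many crossings go uncounted, by simulation.** From the documents: 70 patients per arm (Protocol 7.5) and 16 post-baseline time points (SAP Table 6.7:1). Assumed, because the documents give no PR data: normal distributions, baseline mean 150-165 msec, between-patient SD 18-25, within-patient SD 6-12, mean shift 0-40. A new crossing means baseline ≤ 200 and highest on-treatment PR > 200. The central case is mean 160, SD 22, within-patient SD 8 and 16 readings. Its counts are per 70 patients with baseline ≤ 200. Counted = new × (1 − uncounted share).

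| Mean shift (msec) | Uncounted share, 1 reading | Uncounted share, 16 readings | Central: new crossings | Central: uncounted share | Central: counted |
|---|---|---|---|---|---|
| 0 | 91-100% | 85-100% | 6.1 | 99.5% | 0.03 |
| 5 | 88-100% | 78-100% | 9.5 | 98.8% | 0.1 |
| 10 | 83-100% | 69-100% | 14.3 | 96.0% | 0.6 |
| 20 | 70-99% | 45-95% | 25.8 | 78.6% | 5.5 |
| 30 | 54-91% | 22-63% | 38.8 | 43.5% | 21.9 |
| 40 | 37-60% | 8-17% | 50.7 | 11.9% | 44.7 |

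Most crossings go uncounted throughout the assumed range up to a shift of about 10 msec, and in nearly all of it at 20. At 30 msec the answer depends on the assumptions. At 40 msec with repeated readings, most crossings are counted.

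**Step 3: the AE route.** SAP 7.8.1 tabulates all AEs by preferred term with no attribution filter. Entry, however, depends on reporting. SAP 7.8.4 makes an abnormal ECG finding an AE only if the investigator judges it clinically relevant. Protocol 5.2.4 contains a statement to that effect and also one that any new or worsened finding is recorded as an AE. Until these are reconciled, the AE tables cannot be relied on to count every new PR above 200 msec.

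**The case against.** A reader might infer that conduction disorders are counted only through the PR rule and the filtered morphology table. The documents do not support that. The QRS row bears on bundle branch block, AEs are tabulated without a filter, PR and QRS are summarised over time, and high values are flagged in listings. The mean-change table can be sensitive. With a 5 msec shift and within-patient SD 8, the standard error of the between-arm difference in change at one visit is 8 × √2 × √(2/70) ≈ 1.9 msec, so the shift is about 2.6 standard errors. This stands as partial coverage. It does not give the number of patients who crossed, and flagged listings are not by-arm counts.

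A reader might also infer that rows will be chosen after unblinding. No text plans that, and AV block and bundle branch block, as class effects named in the protocol, would plausibly pass the filter. SAP 5.4.1 might also narrow the gap. What remains is that the visible wording does not fix the rows in advance.

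Finally, the joint rule is a specificity choice, also used for HR and QRS, and an unconditional row would be noisy. In the central case, 6.1 of 70 patients cross with no shift and 9.5 with a 5 msec shift, which is hard to separate descriptively. That is a reason to keep the existing row and place the new one beside it.

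**Conclusion.** The point holds in a limited form. It follows from the visible wording alone that no table counts a new PR above 200 msec without the 25% rise, that baselines above 160 and up to 200 msec are affected, and that the morphology filter has no stated criterion. The tempting general claim that most new PR above 200 msec is missed is not a fact in the documents. It rests on assumed PR distributions, holds for mean shifts up to about 10 msec, fails at large shifts, and concerns the interval table only. First-degree AV block could still appear in the morphology or AE tables. Everything said about missing criteria is subject to SAP 5.4.1, which is not in the available text. Likewise, the Protocol 1.4.2 statement that criteria are defined sits in a risk-mitigation table and does not promise a particular analysis. This is a worthwhile, inexpensive tightening of the safety tables and does not affect the primary analysis.

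**What to change.** Before database lock, in SAP 7.8.4:

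1. Delete the attribution condition from the morphology sentence. Tabulate every new-onset morphological finding by treatment group, using the SAP's own definition (on treatment, not reported at baseline).
2. Beside the existing notable-PR row, add *new onset of PR > 200 msec on treatment (baseline ≤ 200 msec)*, with no percentage condition.

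Also reconcile the statements in Protocol 5.2.4 and SAP 7.8.4 on when a new ECG finding becomes an AE.

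The two table changes use data already collected. They cost a wording change, one extra row and a longer morphology table. The PR row will include chance threshold crossings in every arm, about 6 of 70 with no drug effect in the central assumed case, so it must be read against placebo.

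### SAP 7.8.4 checks whether Fridericia's correction fits but links no supplementary corrected QT result to the answer; minor, and of consequence only if heart rate differs between arms and the exponent is away from 1/3

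*SAP*

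**What the plan says.** Under its heading on the appropriateness of the correction methods, SAP 7.8.4 plans two random-coefficient models, each fitted to off-drug values (placebo patients) and to each dose group separately.

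- The first: "To evaluate the appropriateness of the heart rate correction methods, the slope of the relationship of the (untransformed) QTcF interval versus RR interval".
- The second: "The slope of the relationship of the log-transformed (uncorrected) QT interval versus log-transformed RR interval will be estimated for off-drug values".

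For both, the reported result is the same: "The population estimate of the slope together with its two-sided 95% confidence interval will be displayed in a footnote to the plot". No slope is named that would show a poor fit, and no analysis is tied to the result.

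The displays are set out earlier in 7.8.4. Descriptive statistics over time cover the "quantitative ECG variables: QTcF, HR, QT, QRS, PR". The categories include "Maximum change from baseline of QTcF ≤ 30 msec, > 30 to ≤ 60 msec, or > 60 msec on treatment", together with new onset of QTcF above 450, 480 and 500 msec. QTcF also carries its own notable findings, the shift table and the plot of baseline against maximum change. For the one other correction mentioned, the SAP says: "For QTcB and RR, only listings will be provided".

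Uncorrected QT has its own descriptives, a new-onset category above 500 msec (also a notable finding) and a change category split at 60 msec. Heart rate has descriptives and a notable-finding rule. The ECG derivations are referred to SAP Section 5.4.1, which is not in the public text.

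Protocol 1.4.2 lists cardiac disorders among the trial risks and notes that "criteria for heart rate, QT prolongation and cardiac conduction disorders are defined".

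**The concern.** Fridericia's formula divides QT by RR to the power 1/3. If QT in this population follows RR with a different exponent, QTcF still depends on heart rate. That does little harm while heart rate is similar across arms. If the drug changes heart rate, the residual dependence appears as a difference in QTcF between active and placebo, in either direction.

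The protocol treats heart rate as something to watch: an entry limit in Section 3.3.3, a tachycardia criterion in 3.3.4.1 and graded sinus tachycardia in 5.2.6.1.6. SAP 7.4.1 says the phase 3 dose choice will weigh tolerability and safety alongside efficacy. A QTcF artefact could therefore colour one input to that choice. The planned check could reveal the problem, but nothing in 7.8.4 supplies a better-corrected result to read in its place. A correction chosen after unblinding is open to the charge of selection.

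**Working it through.** The documents give no expected QT effect, heart-rate change or ECG sample size, so there is no planned figure to reproduce. The check below sizes the possible artefact.

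**Inputs from the documents.** There are 70 patients per arm (protocol 7.5). SAP Table 6.7:1 has 16 post-baseline windows: 9 in dose escalation (weeks 2 to 18) and 7 in maintenance (weeks 20 to 46). The change categories use the maximum over all on-treatment values. Baseline is a single ECG (SAP 7.8.4).

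**Assumptions, not in the documents.** QTcF is 410 msec at 70 bpm, heart rate rises by 10 or 20 bpm, and the true exponent b lies between 0.25 and 0.40. The drug has no effect on repolarisation.

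**Step 1: artefact.** If QT is proportional to RR^b, then QTcF is proportional to RR^(b - 1/3). A rise in heart rate from HR0 to HR1 then gives

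artefact = 410 x ((HR0/HR1)^(b - 1/3) - 1).

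For b = 0.25 and 70 to 80 bpm: 410 x (0.875^(-0.0833) - 1) = +4.6 msec. For b = 0.40: 410 x (0.875^(0.0667) - 1) = -3.6 msec.

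| True b | 70 to 80 bpm | 70 to 90 bpm |
|---|---|---|
| 0.25 | +4.6 | +8.7 |
| 0.30 | +1.8 | +3.4 |
| 1/3 | 0 | 0 |
| 0.37 | -2.0 | -3.8 |
| 0.40 | -3.6 | -6.8 |

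A positive value is false prolongation; a negative value hides a true rise.

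**Step 2: patients with a maximum change above 30 msec.** Treat readings as independent normal values with within-patient SD s (assumed 8 or 10 msec), one of them the shared baseline. With artefact d at all 16 readings,

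P = 1 - integral of phi(z) x Phi((30 - d)/s + z)^16 dz.

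If d applies only to the 7 maintenance windows, the last factor becomes Phi((30 - d)/s + z)^7 x Phi(30/s + z)^9.

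| Artefact (msec) | s = 8, all 16 | s = 8, last 7 only | s = 10, all 16 | s = 10, last 7 only |
|---|---|---|---|---|
| -3.6 | 1.8% | 3.2% | 8.2% | 11.7% |
| 0 | 4.2% | 4.2% | 13.9% | 13.9% |
| +1.8 | 6.2% | 5.1% | 17.6% | 15.6% |
| +4.6 | 10.8% | 7.5% | 24.6% | 19.4% |

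In 70 patients, with s = 8, +4.6 msec adds between 70 x (0.075 - 0.042) = 2.3 and 70 x (0.108 - 0.042) = 4.6 flagged patients.

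**Step 3: other thresholds, single reading.** Take absolute QTcF as normal with mean 410 and SD 18 msec (assumed). The share above 450 msec is 1.3% with no artefact, 2.5% at +4.6 and 0.8% at -3.6. The share with a change above 60 msec stays at or below about 0.01% for an SD of change of 10 to 15 msec, so that category hardly moves.

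**Step 4: why significance would be a poor trigger.** Suppose the off-drug exponent had a standard error of about 0.01 (an assumed-variance estimate). A 95% interval would then exclude 1/3 once b departs from it by 1.96 x 0.01 = 0.0196. By the Step 1 formula that is 1.1 msec at +10 bpm and 2.0 msec at +20 bpm. Such a rule would fire for trivial misfit.

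**The case against.** Several points count against a stronger reading, and most of them stand.

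- A reader might infer that all QT tables rest on QTcF. They do not: uncorrected QT and heart rate have their own. These do not close the gap, because uncorrected QT shortens as heart rate rises and can itself mask prolongation.
- A reader might infer that no other correction is planned at all. The documents do not allow that conclusion, since Section 5.4.1 is not public. What can be said is that 7.8.4, which sets out the displays, shows none.
- A reader might infer that the QTcF comparison is biased. That needs both a heart-rate difference between arms and an exponent away from 1/3, and the documents give neither. The class effects named in protocol 1.2 are conduction disorders and QT prolongation, with no size of heart-rate change.
- A full shift at every reading overstates the effect. Nine of the 16 windows fall in escalation, and every active arm starts at the same low dose.
- Safety analyses are descriptive, without hypothesis tests (protocol 7.2.5). Slopes with intervals are shown off-drug and by dose group, and RR and QTcB are listed, so a misfit would be visible to a careful reader.

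What remains is that a visible misfit would leave the reader with no better-corrected table, although the exponent needed for one is already being estimated.

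**Conclusion.** The point holds in a limited, conditional form. In the available text of SAP 7.8.4 the fit of the correction is examined, the answer goes to a plot footnote, and all corrected displays remain on QTcF whatever it shows.

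Under the assumed values, a 10 bpm difference in heart rate gives an artefact between about +4.6 and -3.6 msec. Mean changes, counts above 30 msec and counts near 450 msec would be affected; counts above 60 msec would hardly change. If heart rate does not differ between arms, or the exponent is close to 1/3, the effect is negligible. The counts also depend on the assumed within-patient SD and on independent readings.

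The documents do not make this comparison the deciding QT conclusion for dose selection; safety is one of several inputs. The primary endpoint is not touched. Severity: minor.

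**What to change.** In SAP 7.8.4, with the derivation beside the other ECG derivations, add QTcP = QT / RR^b. RR is in seconds and b is the off-drug (placebo) slope from the log(QT)-log(RR) model already planned. Show the change-over-time summary, the >30/>60 msec change categories and the >450/>480/>500 msec categories on QTcP beside QTcF, as a supplementary display.

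Do this either always, or when a pre-stated size of misfit is reached. A workable rule computes the implied artefact, mean QTcF x ((HR placebo / HR active)^(b - 1/3) - 1), from the estimated b and the observed heart rates. The tables are added when its absolute value exceeds a number of msec fixed before unblinding. The trigger should not be whether a confidence interval excludes zero, for the reason in Step 4.

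QTcF stays the main display. The cost is SAP wording, one derived variable and a small set of extra descriptive tables. No new data are needed.
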